## **Direct Benefits to Subjects**

## Direct Benefits to Subjects

This study was not designed to benefit participants directly. However, we have shown that drug use significantly declines after participation in our inpatient laboratory studies: specifically, 58% of participants reported a nearly 50% decrease in use from pre-admission levels (Roux et al., 2012).

## Compensation and/or Reimbursement

Will compensation or reimbursement for expenses be offered to subjects?

Yes

Please describe and indicate total amount and schedule of payment(s).

Include justification for compensation amounts and indicate if there are bonus payments.

Participants are compensated (in Cash) for each visit of the screening process (\$25-50/visit, depending on its duration) for approximately 3 visits plus \$50 for the follow-up visit. If a participant is disqualified prior to their in-person screening, their compensation may be sent to them in the form of an Amazon gift card or will be wired to them.

Participants will be paid \$25/day with a \$50/day bonus for completion of the study. Use of a per diem bonus is necessary to keep participants from leaving the study during the last several days when the money remaining to be earned would otherwise be proportionally small.

Payments will be separated into several installments (\$600 per week) at the end of the study in order to prevent large one-time payments. To minimize the number of visits to NYSPI to receive their study compensation, participants may request wire delivery of their \$600 payments using a secure service like Western Union.

Total payments for study completers will be approximately **\$1,200-1,700**.

## Uploads

Upload copy(ies) of unbolded Consent Form(s)

Screening Consent 8061 18 OCT 2022 (No Changes).pdf

Study Consent 8061 18 OCT 2022 (Clean).pdf

Upload copy(ies) of bolded Consent Form(s)

Study Consent 8061 18 OCT 2022 (Bold).pdf

Upload copy(ies) of recruitment materials/ads to be reviewed

Upload evidence of FDA IND approval(s)

Upload a copy of Certificate of Confidentiality

Upload copy(ies) of the HIPAA form

Upload any additional documents that may be related to this study

Khangura and Walters 2022.pdf

STATISTICAL ANALYSES

Data Analysis Plan: The distributions of all continuous variables will be checked for normality, and transformations will be employed (if necessary) before applying specific parametric techniques. Before performing specific analyses, we will examine all outcomes for outliers. All statistical comparisons will be two-sided and the critical level for rejection of the null hypothesis will be considered to be a p-value of < 0.05 . Where needed, False Discovery Rate Analysis will be used to adjust critical p values to control for multiple comparisons. Any comparison where homogeneity is violated will not be considered significant. Means, standard deviations, proportions, and 95% confidence intervals will be used to describe all continuous variables.

Dropouts and Missing Data: As this is an inpatient laboratory study within a controlled setting, we expect only minimal intermittent missing data, though we do expect to have some subjects drop out without completing all of the experimental conditions. We will use all available data from subjects prior to drop-out. We will account for missing data directly using mixed-effects models (MEM) (Diggle et al. 2002). MEMs do not require complete measurements to estimate effects and inferences are valid provided that data are “missing at random” (Little & Rubin, 2002). ‘Missing at random’ (i.e. the missing mechanism does not depend on the value of the unobserved outcome) is un-testable in most medical research and in our study as well. One can assume either parametric or semi-parametric models for the missingness that does depend on the unobserved outcome value and do the analysis (Diggle and Kenward 1994, Kenward 1998). Comparison of the inferences from assuming various models for the missingness provides a measure of the validity of the efficacy estimate from the model that assumes missing ‘at random’. One can also compute a local sensitivity index which measures the change in the estimated treatment effect in a neighborhood of the ‘missing at random’ model for missingness (Rotnitzky et al. 1998). We will perform sensitivity analyses based on these two approaches to assess the effect of the assumption of missing ‘at random’ on the inference.

Randomization: Once a participant is enrolled, a randomization sequence table will be generated by a blinded statistician. The table will determine the order of testing of the various dose combinations of dronabinol (.00, .35, and .70 mg), and naloxone (0.0, 0.2 and 0.4 mg).

Aims, Outcome Measures, and Hypotheses

Primary Aim: Assess the ability of inhaled dronabinol to alter the severity of naloxone-precipitated withdrawal.

- The primary dependent variable (DV) for this aim will be the total opioid withdrawal score from the testing session. Repeated-measures analysis of variance (ANOVA) will be used to assess differences among the various dose conditions.
- We hypothesize that there will be a dose-dependent effect of dronabinol to attenuate the severity of naloxone-precipitated withdrawal.

Secondary Aim: Assess the safety of inhaled dronabinol in combination with naloxone.

- The primary DVs are the SAFTEE (AEs not related to withdrawal) and physiological parameters. Generalized mixed-effects models with participant as a random effect and an autoregressive correlation structure for the within-participant observations will be used to analyze the total number of AEs and their severity.
- We hypothesize that dronabinol, in combination with naloxone, will produce more AEs than placebo but less than naloxone alone.

Secondary Aim: Assess the impact of inhaled dronabinol on naloxone's effects on pupil diameter (i.e., μ -opioid receptor blockage).

- The primary DV will be pre-to-post- medication change in pupil diameter from each testing session. Repeated-measures ANOVA will be used to assess differences among the various dose conditions.
- We hypothesize that dronabinol will not significantly alter naloxone's effects on pupil diameter (in comparison to placebo).

Secondary Aim: Assess the abuse potential of inhaled dronabinol.

- The primary DV will be pre-to-post- medication change in positive subjective drug ratings such as drug "Liking" and "Good Effect."
- We hypothesize that self-reported dronabinol "Liking" will not be significantly greater than placebo.

Power

To approximate a suitable number of subjects for a traditional hypothesis-testing approach, a power analysis was conducted using G* Power 3.1.7. Estimates of the magnitude of the medication effect on withdrawal were estimated using a previous study that assessed naloxone-precipitated withdrawal (Jones et al., 2016). Based on these data we calculated a Cohen's D effect size of .75, which constituted a 15-point difference (mean SD of 20) in total withdrawal score (0-125) between any two dose conditions. Applying this to the current proposal, a total sample size of 16 completers should provide 90% power to detect this difference at a p of < 0.05 . Sixteen completers will provide 88% power to detect a 10-mm difference in positive subjective effects, e.g. "Liking" on a 100-mm VAS scale (alpha of 0.05). This analysis assumes a SD of 12 mm and a Cohen's D effect size of 0.84 based on previous visual analog scale assessments of abuse liability of opioids and cannabinoids (Cooper et al., 2018, Jones et al., 2017).

Due to the exploratory nature of this study, effect size estimates will be the main research outcome for the secondary aims, along with the interpretation of confidence interval lengths and degree of overlap to indicate precision and degree of difference (i.e., threshold of clinical importance) between dose conditions (respectively). A sample size of 16 completers was determined to be sufficient to obtain precise 95% confidence intervals with a margin of error of at most 25%. Thus, with regard to the detection of differences in all the study aims, these calculations suggest that this study is suitably powered.

Sex as a Biological Variable

Sex-specific comparisons will be performed to provide an indicator of a Sex x Treatment interaction. The within-subject nature of the study's design should control for potential sex differences. Though not powered to specifically detect sex differences, we are still in compliance with NIH policies to enroll males and females. Furthermore, sex as a biological variable will be examined and reported in accordance with NIH policy (https://orwh.od.nih.gov/sites/orwh/files/docs/NOT-OD-15-102_Guidance.pdf).

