**Admission and Morphine Stabilization:** Once eligibility is determined, participants will be admitted into the secure NYSPI inpatient unit for the duration of the study (approximately 4 weeks). Following admission, participants will begin 5-14 days of stabilization on oral morphine (30 mg, QID: 700, 1300, 1800, 2200 hrs). Additionally, 10-20mg PO hydromorphone doses will be available PRN to address withdrawal symptoms insufficiently managed by oral morphine and supplemental medications alone (to a maximum of 80 mg per day). Hydromorphone will be available in addition to QID oral morphine when deemed clinically appropriate by the study physician. **The participant must exhibit at least "mild" opioid withdrawal according to the COWS (score >8).** Once stabilized, participants will receive oral morphine daily (30 mg) at 700, 1300, 1800, and 2200 hrs. **Prior to the initiation of testing sessions, stability on morphine will be established. Stability will be defined as participants exhibiting a mean COWS score not exceeding 5, with no hydromorphone administration.** Vitals and Respiratory Rate will be assessed immediately before and for one hour (in 15-minute intervals) following the additional dose to ensure against oversedation.

Common clinically used medications such as, clonidine, zolpidem, and Compazine will be available, along with methocarbamol (750-1500 mg, every 6 hours, not exceeding 6000mg in 24 hours). The use of these medications will be suspended by 6 PM the day before a lab session. Participants who cannot stabilize and will be discharged and offered the same end-of-study treatment options described below.

**Safety Session:** Testing will not begin until withdrawal symptoms are no longer present, based upon the Clinical Opioid Withdrawal Scale (COWS: Handelsman et al., 1987). Prior to testing vaped marijuana in combination with intranasal (IN) naloxone, participants will complete a Safety Session. During the safety session, they will receive a test dose of vaped marijuana (25 mg). If a participant's vital signs exceed any of the following benchmarks outlined in the Criteria for Early Discontinuation, they will be discontinued from the trial (Table 1).

Table 1: Study Design														
Week 1							Week 2							
	Mon	Tue	Wed	Thu	Fri	Sat	Sun	Mon	Tue	Wed	Thu	Fri	Sat	Sun

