	Admission	Stabilization	Stabilization	Stabilization	Stabilization	Stabilization	Stabilization	Stabilization	Stabilization	Stabilization	NLX 0mg + V-MJ 0mg	NLX 4mg + V-MJ 25mg		
Week 3							Week 4							
	NLX 0mg + V-MJ 12.5mg	NLX 0mg + V-MJ 25mg	NLX 4mg + V-MJ 12.5mg	NLX 4mg + V-MJ 0 mg			Discharge							

**Laboratory Testing:** Laboratory testing sessions will consist of a modified naloxone challenge procedure (A.K.A. Wang Test: Wang et al., 1974). The challenge begins with baseline assessments. Ten common symptoms of opioid withdrawal (gooseflesh, vomiting, tremor, sweating, restlessness, lacrimation/nasal congestion, yawning, warming/cooling sensations, stomach pain, and muscle ache) will be assessed by a research assistant trained in administering the SOWS/COWS. For safety, the physician or nurse who is providing medical oversight will directly observe its administration.

Each symptom is coded as either “absent” or “present,” with between 1 and 6 points added when a symptom is observed (Table 2). Following pre-test assessments, a physician or nurse practitioner will administer the study drug combination (1000-1100 hrs). Assessments of withdrawal are made at 10-minute intervals for 50 minutes. The total withdrawal score is calculated at the end of the session. To minimize carry-over effects, sessions will be conducted at least 48 hours apart (>5 half-lives of both medications). See Table 1 for an example dosing schedule. The following dose combinations of vaped marijuana (V-MJ) and IN naloxone will be tested in random order:

- Naloxone 0 mg + V-MJ 0.0 mg
- Naloxone 0 mg + V-MJ 12.5 mg
- Naloxone 0 mg + V-MJ 25 mg
- Naloxone 4 mg + V-MJ 0.0 mg
- Naloxone 4 mg + V-MJ 12.5 mg
- Naloxone 4 mg + V-MJ 25 mg

Signs and Symptoms	Table 2: Rating Scale for Opioid Withdrawal											
	(Pre-test)		Time after first naloxone dose									
	0 min		10 min		20 min		30 min		40 min		50 min	
Signs and Symptoms	Present	Absent	Present	Absent	Present	Absent	Present	Absent	Present	Absent	Present	Absent
Gooseflesh	6	0	3	0	3	0	2	0	1	0	1	0
Vomiting	6	0	3	0	3	0	2	0	1	0	1	0
Tremor	6	0	3	0	3	0	2	0	1	0	1	0
Sweating	6	0	3	0	3	0	2	0	1	0	1	0
Restlessness	4	0	2	0	2	0	1	0	1	0	1	0
Lacrimation/ Nasal Congestion	4	0	2	0	2	0	1	0	1	0	1	0
Yawning	4	0	2	0	2	0	1	0	1	0	1	0
Feeling of Change in Temperature	3	0	1	0	1	0	1	0	1	0	1	0
Stomach Pain	3	0	1	0	1	0	1	0	1	0	1	0
Muscle Ache	3	0	1	0	1	0	1	0	1	0	1	0
Actual time of observation												
Scores												
Pupil Diameter												

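### The SAP declares any comparison with violated homogeneity non-significant, which can void a valid primary result that a standard method would handle

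*SAP*

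**What the plan says.** The SAP's Data Analysis Plan sets two-sided tests at p < 0.05 and then adds: "Any comparison where homogeneity is violated will not be considered significant". No outcome is exempt. Under Primary Aim, the total withdrawal score is analysed as follows: "Repeated-measures analysis of variance (ANOVA) will be used to assess differences among the various dose conditions". The primary outcome is therefore covered.

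Neither document says whether homogeneity means equal condition variances or sphericity, which test decides it, at what threshold, or what analysis follows a failure. The nearby remedies serve other purposes:

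- Transformation belongs to the normality check: "transformations will be employed (if necessary) before applying specific parametric techniques".
- False discovery rate adjustment is for multiplicity.
- Mixed models, under Dropouts and Missing Data, are for missing data.
- The autoregressive mixed model under the safety aim is for adverse events.

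Description is kept whatever the test result: "Means, standard deviations, proportions, and 95% confidence intervals will be used to describe all continuous variables".

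The Protocol (Study Procedures, Laboratory Testing) lists six conditions, three of them without naloxone. Its Safety Session paragraph says: "Testing will not begin until withdrawal symptoms are no longer present".

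**The concern.** The rule turns a correctable assumption into a fixed negative verdict, whatever the p-value. A paired contrast, such as naloxone 4 mg with active against placebo marijuana, uses the standard error of the within-participant differences. That is valid whether or not the two conditions have the same spread, so the rule can discard a sound test.

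The SAP's Power section sizes the trial for a conventional hypothesis test of the primary outcome. The significance conclusion on the primary hypothesis is what is at stake. Because neither the type of homogeneity nor the test is named, that conclusion could also turn on a choice made after the data are seen.

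The design gives a plausible trigger. Sessions without naloxone, in participants whose withdrawal has settled, should score near zero and may vary less than naloxone 4 mg sessions.

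**Working it through.** **Inputs from the documents.** 16 completers, two-sided 0.05, a 15-point difference and a mean SD of 20 (SAP, Data Analysis Plan and Power); six conditions (Protocol, Laboratory Testing). The SAP's Randomization paragraph lists a different, three-by-three dose grid. That mismatch is a separate matter to reconcile; the Protocol's six conditions are used here.

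**Assumptions.** Condition-specific SDs, the within-participant correlation r, normal data, and the homogeneity test (median-centred Levene, mean-centred Levene or Pitman-Morgan, each at 0.05).

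**Step 1: the plan's own figure.** The SAP gives no figure for this rule, only 90% power. A two-sided paired t-test with standardised difference 15/20 = 0.75 and 15 df gives 80.1%; one-sided it gives 88.8%. Two-sided 90% is reached if 20 is a per-condition SD and r is about 0.63. That gap is a separate issue. The baseline below is r = 0.5, where the SD of the difference equals 20.

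**Step 2: two conditions, homogeneity judged on those two.** SD of the difference = √(s₁² + s₂² − 2·r·s₁·s₂). For 24/16 and r = 0.5 this is √(576 + 256 − 384) = √448 = 21.2, so the standardised difference is 15/21.2 = 0.71. For 20/10 it is √(400 + 100 − 200) = 17.3, giving 0.87. The 'with the rule' column is the simulated share with paired p < 0.05 and homogeneity not rejected; its range is over the three tests.

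| SDs | Without the rule | With the rule |
|---|---|---|
| 20/20 | 80% | 76-78% |
| 22/18 | 78-79% | 68-75% |
| 24/16 | 76% | 46-62% |
| 20/10 | 90% | 16-39% |

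The paired t-test's own type I error stays at 4.8-5.2% throughout, so the rule gives this contrast no protection it needs.

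**Step 3: homogeneity judged over all six conditions.** With naloxone 4 mg SDs of 20 and r = 0.5, the same contrast starts at 80-81%. With the rule it falls to 67-72% if the naloxone 0 mg SD is 15, 31-57% if 12, 7-32% if 10, and 0-1% if 7. This applies a six-condition check to a two-condition contrast, so it is a secondary scenario.

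**Step 4: would deleting the sentence be enough?** Take no true effect, a one-way six-condition ANOVA, naloxone 0 mg SD 7-10 against 20, and r 0.3-0.7. Simulated type I error:

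- uncorrected omnibus test: about 6.5-8.3%
- Greenhouse-Geisser omnibus test: about 4%
- pooled-error contrast between two naloxone 4 mg conditions: about 7-12%
- pooled-error contrast between two naloxone 0 mg conditions: 0-0.2%
- paired contrast: about 5%

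Deletion alone would leave an inflated omnibus test and pooled contrasts that are wrong in both directions. In a 2×3 analysis of the same data, the marijuana main effect and the interaction hold 4.8-5.3%, so that form is not inflated by this pattern.

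**The case against.** Much of the opposing case stands.

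- The rule acts only when a violation is found. With equal SDs the primary contrast loses just 2-4 points.
- The sentence speaks of each comparison. On its natural reading, low spread at naloxone 0 mg does not touch a contrast between two naloxone 4 mg conditions.
- The floor argument is inference. Stability is defined as a mean COWS not exceeding 5, so some symptoms may remain, and that threshold is on COWS, not on the Table 2 score. No condition-specific SD is given.
- For the primary aim the error is conservative: it can remove a significance label but cannot create a false positive. Estimates and confidence intervals survive.
- A transformation triggered by non-normality may soften the loss. In a simulation of Table 2 item scores under assumed effects (post-dose columns only, mean falling from 38 to 13), power with the rule was 50-61% untransformed and 79-92% with a square root. With a log it was 41-66%, so this is not dependable.

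A reader might infer that the rule slants the secondary aims, because a forced non-significant label would agree with the pupil hypothesis ("We hypothesize that dronabinol will not significantly alter" naloxone's effect) and with the Liking hypothesis. The direction is right, but the Power section makes effect sizes and intervals the main secondary outcome, so the harm is limited.

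None of this supplies a reason to void a valid paired test.

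**Conclusion.** Wrong as written. The sentence is unqualified, reaches the primary outcome and is softened nowhere else. Judged on the two conditions compared, its cost runs from 2-4 points of power at equal SDs to more than half the power at 20/10. The figures rest on assumed SDs, r = 0.5, normal data and the choice among three homogeneity tests.

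Two stronger readings are tempting, and the documents support neither:

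- **The rule will almost certainly erase the primary result.** The near-total losses need a six-condition check and a much smaller spread without naloxone. That is plausible, but not shown.
- **The planned ANOVA is generally anti-conservative without the rule.** The SAP does not say whether the ANOVA is one-way or 2×3. The omnibus inflation belongs to the one-way form, and pooled contrasts err in either direction depending on the pair.

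**What to change.** Replace the sentence with: *Unequal variances or failed sphericity will not by themselves make a result non-significant. Repeated-measures ANOVA tests with more than one numerator degree of freedom will use a Greenhouse-Geisser correction, and dose contrasts will use contrast-specific (paired within-participant) error, not the pooled ANOVA error.* The last clause is needed because Greenhouse-Geisser does not correct pooled contrasts.

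An alternative is to use the mixed model the SAP already names for missing data, with condition-specific variances and small-sample degrees of freedom.

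The cost is one SAP sentence and slightly more analysis. Each paired contrast has 16 − 1 = 15 error df, instead of (6 − 1)(16 − 1) = 75 in a one-way six-condition ANOVA, so the critical t is 2.13 instead of 1.99. Greenhouse-Geisser is mildly conservative here, and the mixed model's extra variance parameters would be imprecise with 16 participants.

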## Funding Source #1

Is the PI of the grant/contract the same as the PI of the IRB protocol?

Yes

Select one of the following

The grant/contract is currently funded

Source of Funding

Federal

Institute/Agency

National Institute on Drug Abuse

Grant Name

The Ability of Inhaled Dronabinol to Reduce the Severity of Naloxone-Precipitated Withdrawal.

Grant Number

R21 DA049076-01A1

Select one of the following

Single Site  
Business Office  
RFMH

Does the grant/contract involve a subcontract?

No

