## Lay Summary of Proposed Research

### Lay Summary of Proposed Research

To address the opioid epidemic, there has been an increased focus on the development of novel medications to treat opioid use disorder (OUD). However, a pharmacological approach more specific to overdose harm reduction (i.e., minimizing the harmful effect of drugs among active users) may be to increase the tolerability of the overdose reversal agent, naloxone (NLX). In emergency settings, NLX administration (in suspected cases of opioid overdose) often results in violent patient behavior, as individuals who are opioid dependent awaken in a state of opioid withdrawal (Gaddis and Watson, 1992; Osterwalder, 1996).

Naloxone-induced withdrawal is also common in out-of-hospital settings in which non-medical persons are asked to administer naloxone to save the lives of their peers. Analysis of the Opioid Lab's overdose reports from the individual who administered NLX found that 98% of overdose victims presented notable opioid withdrawal-related adverse events (AEs) including: nausea, abdominal pain, vomiting, joint/muscle pain, and tremor. Concerns of the adverse effects of NLX administration may prevent or delay the use of this life-saving intervention.

The goal of the proposed, proof-of-concept study is to test the combined effects of vaporized marijuana [Delta-9-tetrahydrcannabinol (THC)] with NLX as a proof of concept towards the possible development of a combined overdose reversal agent with improved tolerability. Marijuana will not actually be vaped per se, but a “vaporizer” will be used to produce an aerosol from marijuana plant material, which the participant will inhale. Marijuana plant material will be obtained from the National Institutes on Drug Abuse (NIDA). In clinical studies, oral synthetic THC (Bisaga et al., 2015; Lofwall et al., 2016) reduced the severity of opioid withdrawal during opioid detoxification (Scavone et al., 2013). Clinically, cannabinoid drugs like Marinol® (oral synthetic THC), Sativex ® (nabixomols), and Cesamet® (nabilone) are used to treat nausea and vomiting, common symptoms of opioid withdrawal. This study will investigate the ability of vaporized marijuana (V-MJ) (0.00, 12.5, and 25 mg; concentration= 11.7% THC + 0.04% CBD.) to reduce the severity of opioid withdrawal precipitated by intranasal (IN) NLX (0.0 and 4.0 mg). The final dose of marijuana will be achieved in 10 puffs/vapes, in 10-12 minutes (at a temperature of 210°C).

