How cannabinoids may help? The endocannabinoid system is a potential novel target for reducing opioid withdrawal severity. Studies show that opioid and cannabinoid receptors are co-localized in multiple brain regions. Both receptors also have cross-modulatory pharmacological effects including: cross-agonism, -antagonism, -sensitization, and -tolerance (Robledo et al., 2008). Preclinical studies have demonstrated that tetrahydrocannabinol (THC) decreases signs of opioid withdrawal in morphine-dependent rodents (Bhargava, 1976; Cichewicz and Welch, 2003; Gamage et al., 2015; Hine et al., 1975). In clinical studies, oral dronabinol (synthetic THC: Bisaga et al., 2015; Lofwall et al., 2016) and smoked cannabis have been shown to reduce the severity of abstinence-induced opioid withdrawal during opioid detoxification or

stabilization (Scavone et al., 2013). Clinically, cannabinoid receptor type-1 agonists such as, Marinol® (oral synthetic THC), Sativex® (nabixomols), and Cesamet® (nabilone) are used to treat nausea and vomiting, common symptoms of opioid withdrawal. Joint and muscle pain are also common AEs associated with NLX-precipitated withdrawal. In clinical laboratory investigations of their analgesic effects, cannabinoids have shown promise in treating muscle pain (Cooper et al., 2013 & 2018).

**Rationale:** This study will investigate the ability of vaporized marijuana (V-MJ) (0.00, 12.5, and 25 mg: concentration= 11.7% THC) to reduce the severity of opioid withdrawal precipitated by intranasal (IN) NLX (0.0 and 4.0 mg). If our hypotheses are supported, this study may suggest that the combination of an intranasal opioid receptor antagonist with a cannabinoid receptor agonist may have clinical utility as an overdose reversal medication that is more tolerable than naloxone alone. Reducing the adverse effects of naloxone administration may increase its utilization while minimizing risks for the administrator and recipient.

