## **Specific Aims and Hypotheses**

### Specific Aims and Hypotheses

**Primary Aim:** Assess the ability of vaped marijuana to alter the severity of naloxone-precipitated withdrawal. We hypothesize that there will be a dose-dependent effect of vaped marijuana to attenuate the severity of naloxone-precipitated withdrawal.

**Secondary Aim:** Assess the safety of vaped marijuana in combination with naloxone. We hypothesize that vaped marijuana, in combination with naloxone, will produce more AEs than placebo but less than naloxone alone.

**Secondary Aim:** Assess the impact of vaped marijuana on naloxone's effects on pupil diameter (i.e.,  $\mu$ -opioid receptor blockage). We hypothesize that vaped marijuana will not significantly alter naloxone's effects on pupil diameter (in comparison to placebo).

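### The SAP's randomisation sentence names a product and dose levels that match the protocol only at zero dose of both drugs; as a separate minor matter, the protocol gives two different intervals between sessions

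*SAP*

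**What the plan says.** **Conditions in the SAP.** Under Randomization, the sequence table sets the "order of testing of the various dose combinations of dronabinol (.00, .35, and .70 mg), and naloxone (0.0, 0.2 and 0.4 mg"). No other sentence in the SAP gives levels. For the primary aim, "Repeated-measures analysis of variance (ANOVA) will be used to assess differences among the various dose conditions", and the hypothesis reads "We hypothesize that there will be a dose-dependent effect of dronabinol to attenuate the severity of naloxone-precipitated withdrawal". All four SAP aims name dronabinol.

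**Conditions in the protocol.** The Lay Summary describes "opioid withdrawal precipitated by intranasal (IN) NLX (0.0 and 4.0 mg"). Background, Significance and Rationale gives the other factor as "vaporized marijuana (V-MJ) (0.00, 12.5, and 25 mg: concentration= 11.7% THC"). The primary aim under Specific Aims and Hypotheses is "Assess the ability of vaped marijuana to alter the severity of naloxone-precipitated withdrawal"; the two secondary aims there also name vaped marijuana. Study Procedures (Laboratory Testing) introduces its list with "The following dose combinations of vaped marijuana (V-MJ) and IN naloxone will be tested in random order" and sets out six combinations. The Dose Escalation Safety Pilot uses the same six for the first three participants, in a partly fixed order.

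**Interval between sessions.** The Lay Summary gives 24 hours. Laboratory Testing gives at least 48 hours, on the ground that this exceeds five half-lives of both drugs and so limits carry-over. It refers to Table 1 as an example schedule.

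**The concern.** The SAP's randomisation sentence is the only text in the two documents that says who produces the sequence table and what goes into it; the protocol says only that the order is random. If the content named there is not what the protocol tests, the allocation rule cannot be carried out as written.

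The analysis is affected too. The primary ANOVA refers to dose conditions without listing them, and the only list in the SAP is the mismatched one. The primary question needs naloxone 4 mg given alone and with each marijuana dose, and the SAP's levels contain no 4 mg naloxone.

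The interval conflict is of a different order. A session interval of 24 hours does not meet a minimum of 48, so the two statements cannot both govern scheduling, and the stated protection against carry-over is attached to only one of them.

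**Working it through.** **1. The protocol's own count.** Marijuana {0, 12.5, 25} crossed with naloxone {0, 4} gives 3 × 2 = 6 combinations, which matches the six listed under Laboratory Testing. One is zero of both drugs, leaving 5 active. Three contain naloxone 4 mg.

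**2. Match against the SAP levels.** A zero dose of either cannabinoid product is treated as the same condition (an assumption in the SAP's favour).

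| Protocol condition (naloxone + marijuana, mg) | Naloxone level in SAP {0, 0.2, 0.4}? | Cannabinoid level in SAP {0, .35, .70}? | Obtainable? |
|---|---|---|---|
| 0 + 0 | yes | yes | yes |
| 0 + 12.5 | yes | no | no |
| 0 + 25 | yes | no | no |
| 4 + 0 | no | yes | no |
| 4 + 12.5 | no | no | no |
| 4 + 25 | no | no | no |

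The result is 1 of 6 conditions, 0 of 5 active and 0 of 3 with naloxone 4 mg. It does not depend on whether the SAP intends its levels to be fully crossed.

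**3. Can a different reading remove the mismatch?**

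- *Marijuana as THC content.* At 11.7% THC, 12.5 × 0.117 = 1.46 mg and 25 × 0.117 = 2.93 mg. Neither is .35 or .70 mg, so the overlap is still only 0 + 0.
- *SAP naloxone as a tenfold decimal slip.* The levels become 0, 2 and 4 mg. This recovers naloxone 4 mg alone and nothing else: 4 of 5 active conditions remain missing. It also brings back a 2 mg level that the protocol's Dose Rationale says was dropped.
- *Both together.* The cannabinoid levels still do not meet, so the result is the same as for the slip alone.

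**4. Aims.** The protocol has three: withdrawal, safety and pupil diameter. Each names vaped marijuana where the matching SAP aim names dronabinol. The SAP's fourth aim, abuse potential, has no counterpart in the protocol's Specific Aims and Hypotheses.

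**5. Interval.** Six sessions have five gaps. At 24 hours the first-to-last span is 5 × 1 = 5 days; at 48 hours it is at least 5 × 2 = 10 days. A claim of more than five half-lives holds at 48 hours for half-lives below 48 / 5 = 9.6 hours, and at 24 hours only for those below 24 / 5 = 4.8 hours. The documents give no half-life for either drug, so they do not show whether the justification carries over to the shorter interval.

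**The case against.** The strongest reply is that the SAP text is plainly inherited and nobody would act on it. The grant title is "The Ability of Inhaled Dronabinol to Reduce the Severity of Naloxone-Precipitated Withdrawal", and that is the only place where the protocol still names the inhaled form. The drug section of the protocol and its IND are for marijuana, the six combinations are listed clearly, and the protocol records that a naloxone condition was removed. Read with the protocol, the six listed combinations are the natural content of the SAP's dose conditions.

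Much of this stands. A reader might infer that participants are being randomised to the wrong conditions, or that the primary analysis has no definable content. The documents support neither: no randomisation table is shown, and the protocol supplies a usable list. A reader might also take the SAP to plan a nine-cell design, but that needs full crossing, which the SAP does not state.

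What does not stand is that the likely origin of the text makes it harmless. The SAP is the document that should fix the analysis in advance, and the reader has to override its only list of conditions to apply it.

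On the interval, a reader might infer that sessions at 24 hours would bias the comparison through carry-over. The documents do not show this. The safety-monitoring text expects negligible plasma THC about 2 hours after dosing (30 minutes plus 1.5 hours), and no half-lives are given. Nor should Table 1 be used to decide which interval is followed: the protocol calls it an example, and it is too broken in the available text to count gaps reliably.

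**Conclusion.** The main point holds. The SAP's randomisation rule can yield 1 of the protocol's 6 conditions, none of the 5 active ones and none of the 3 with naloxone 4 mg, and neither alternative reading of the units restores agreement. The mismatch covers product, cannabinoid levels and naloxone levels, and the product mismatch runs through every aim that the two documents share. This must be corrected because it concerns the allocation rule and the content of the primary ANOVA. It is a fault in the documents; no error in conduct or analysis is demonstrated. The conclusion rests on the two texts as they stand and on treating a zero dose of either cannabinoid product as equivalent.

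The interval conflict also holds, but as a minor and separate matter. The protocol contradicts itself, and its carry-over argument covers one of the two intervals. No consequence for the primary comparison is shown, and it adds nothing to the weight of the main point.

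**What to change.** Reconcile the SAP with the protocol so that a single agreed list of conditions (product, levels and combinations) is used for the randomisation table, the aims, the hypotheses and the primary ANOVA. Define the SAP's dose conditions by that list. State whether the abuse-potential aim belongs to the trial, and make both documents agree on it. If a sequence table already exists, check it against the agreed list.

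Separately, reconcile the Lay Summary, Laboratory Testing and the Table 1 example on the interval between sessions, and state the carry-over justification for whichever interval is agreed.

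The cost is a text amendment to the SAP and the protocol. It needs no new data, no change in sample size and no change to the named repeated-measures ANOVA. Which product, doses and interval apply is for the investigators to settle; nothing here favours one over another.
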